14. UNBLINDED AND FINAL ANALYSES

14.1. Unblinded Analysis of Efficacy, Immunogenicity, and Safety

The sequencing of RSV seasons in the Northern and Southern hemispheres lends a natural periodicity which will be reflected in the futility analyses. Futility analyses will be conducted based on data available 30 May (for convenience called “Northern hemisphere,” although a small number of Southern hemisphere subjects may also meet the criteria for inclusion) and on approximately 30 September (for convenience called “Southern hemisphere” or “global season”); and subject to the constraint (applied by the DSMB statistician) that at least 10 cases will have accrued in the active treatment arm. The DSMB will communicate to the Sponsor after each futility analysis its recommendation that the trial is either: a) futile and should be discontinued, or b) should continue enrollment.

When futility (with no requirement for further subject enrollment) has been declared, or Day 180 post-delivery data for efficacy and immunogenicity are available on all delivered infants and maternal subjects, a final Day 180 unblinded analysis of efficacy and immunogenicity, and a preliminary analysis of safety, will be performed upon completion of the last infant D+180 visit and the last maternal postpartum Day 180 visit for all enrolled subjects. This unblinded analysis of efficacy, immunogenicity, and preliminary safety will include all available efficacy, immunogenicity, and safety (inclusive of clinical assessments and concomitant medications) data through the infant D+180 visit and the maternal postpartum Day 180 visit. Treatment codes for this analysis will only be unblinded to the Sponsor statistician after all efficacy and immunogenicity data are monitored, all applicable queries are resolved, and the database is locked without any known critical issues. Safety data will continue to be collected, monitored, and cleaned through the Day 365 visit. The efficacy and immunogenicity data through Day 180, except for the additional immunogenicity testing to be performed post unblinding (e.g., microneutralization assay testing of global season 3 and 4 samples) provided in this analysis will be considered final for the material contained therein, and will not change. In order to execute this unblinded analysis, a select group of study staff will be unblinded at Novavax. No individual unblinded at a subject treatment level will be involved in follow-up safety monitoring. Specifically, personnel at the clinical study site including, investigators and study staff, research site, and study subjects will remain blinded to subject treatment assignments until the end of study for the last infant on post-delivery study D+364.

In addition, an informational analysis of efficacy as specified in the study protocol (Section 10.10.2) may be performed when approximately 25 primary events, i.e., medically-significant RSV LRTI though the first 90 days among the PP-EFF-I population, have accrued. The success criterion is defined as the posterior probability that the event ratio is less than or equal to 1.00 (i.e., Vaccine Efficacy $\geq 0\%$) is greater than or equal to 0.90. This analysis will be performed by the DSMB biostatistician and the IBG in a manner entirely analogous to the analyses for efficacy and futility. The DSMB will communicate the results of the analysis to the Sponsor only in terms of fulfillment or non-fulfillment of the target criterion. Novavax will remain blinded and the outcome will not result in any change in the conduct of the study or the primary efficacy objectives and endpoints.

Results of the unblinded analysis of efficacy, immunogenicity, and safety through Day 180 may be presented by the Sponsor, and may be submitted to the appropriate regulatory authorities as needed.

The final CSR will include all immunogenicity data and safety data (inclusive of clinical assessments and concomitant medications) through the infant subject's D+364 visit, the scheduled end of study. The database will be locked and the final study report prepared, when all of the above data have been entered, reviewed, and all queries related to the data have been addressed.

Modifications or additions to the analyses described above will be included in the SAP. Any decisions to deviate from the planned analyses described in the protocol and in the statistical analysis plan will be described in detail in the final study report.

15. COMPUTER METHODS

The statistical analyses for immunogenicity will be performed using SAS® version 9.4 in a Windows environment. The statistical analyses for the primary and secondary efficacy endpoints may also be performed using R Copyright 2004, The R Foundation for Statistical Computing Version 3.2.4 (2016-03-16) or higher, ISBN 3-900051-07-0.

16. DATA HANDLING CONVENTIONS

All statistical analyses will be 2-tailed and assessed at the 5% significance level.

All output will be incorporated into Microsoft Word (including rtf format) or Excel files, or Adobe Acrobat PDF files, sorted and labeled according to the International Conference on Harmonization (ICH) recommendations, and formatted to the appropriate page size(s).

Tabulations will be produced for appropriate demographic, baseline, and safety parameters. For categorical variables, summary tabulations of the number and percentage of subjects within each category (with a category for missing data) of the parameter will be presented. For continuous variables, the number of subjects, mean, median, standard deviation (SD), minimum, and maximum values will be presented.

For all analyses, a two-sided p-value of < 0.05 (one-sided p-value < 0.025 where appropriate) will be considered statistically significant except for the primary efficacy endpoint, medically significant RSV LRTI through 90 day that will be evaluated using a one-sided p value of 0.0124

All references to analysis of GMEU/GMC/ GMT will be interpreted as analysis of the log (base 10) of EU or concentration values or of the reciprocal titers (e.g., the reciprocal titer of 1:160 is the number 160). Values recorded as below the lower limit of quantitation (LLOQ) of the assay for PCA and anti-F IgG will be set to half LLOQ for the purposes of GMEU/GMC, and GMFR analyses. For MN assays, titers will be reported in International Unit (IU) with the LLOQs of 13 for RSV/A and 8 for RSV/B. Titers below the LLOQs will also be set to half LLOQ, 6.5 IU for RSV/A and 4 IU for RSV/B.

For all data analyses and summary tabulations, categories for analysis and presentation will consist of the RSV F vaccine treatment groups. All descriptive statistical analyses will be performed using SAS statistical software Version 9.3 or higher in a Windows environment, unless otherwise noted. Medical history and AEs will be coded using the MedDRA Version 16.1.

16.1. Random Seeds

For efficacy analyses, random seeds will be set at 200120 with the statement `set.seed(200120)` in R or call `streaminit(200120)` in SAS when appropriate.

16.2. Baseline Definitions

For all analyses, baseline will be defined as the last non-missing measurement prior to the first administration of the study material. For immunogenicity analysis, baseline will be the sample drawn prior to the first vaccination, on the day of vaccination.

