- Document results of any Group B streptococcus (GBS) screening (urine or recto-vaginal swab as applicable), or other infectious disease screening (i.e., for syphilis, gonorrhea, Herpes simplex, chlamydia, HBV, HCV, and HIV).
- Administration of a licensed vaccine recommended during pregnancy, if indicated. *Note: This dose should be administered at least 14 days before or at least 14 days after the Day 0 vaccination.*
- Document current smoking, alcohol, and recreational drug use.
- Document results of gestational diabetes screen.
- Vital signs (blood pressure, pulse, respirations, and axillary body temperature [*Note that repeat testing may be performed for subjects with any abnormality*]), height, and weight;
- Physical examination including the following body systems: HEENT, cardiovascular, pulmonary, gastrointestinal (abdominal), musculoskeletal, lymphatic, and dermatologic; and confirmation of fetal heart tones.
- Blood draw:
 - For RSV baseline serology (20 mL).
 - For subjects participating in the first year in any country: Clinical laboratory assessments (10 mL) for select serum chemistry (i.e., blood urea nitrogen, creatinine, alanine aminotransferase [ALT], aspartate aminotransferase [AST], alkaline phosphatase [ALP], total bilirubin) and hematology (i.e., hemoglobin, white blood cell [WBC], and platelet counts) parameters by central laboratory testing; and HIV, syphilis, HBV, and HCV antigen tests/serologies as required by central or local laboratory testing (i.e., if screening results are not available in prior data collected during the course of the current pregnancy). Since results of the clinical laboratory testing are needed to confirm subject eligibility, it is recommended this phlebotomy be performed at least two days before the planned Day 0 vaccination.
 - For subjects participating in all other years in any country: HIV, syphilis, HBV, and HCV antigen tests/serologies (10 mL, as required) by central or local laboratory if screening results are not available in prior data collected during the course of the current pregnancy.
- Medication history, including concomitant medications.
- Query for any AE experienced since informed consent was obtained.

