6.1.1.3 Day 0 – Vaccination (gestational week 28 to 36^{0/7})

On Day 0, all subjects who have vital signs taken, fetal heart tones checked, and eligibility re-confirmed will be randomized to a treatment group and infant serology cohort. The following procedures will then be performed:

- Query for any AE (and SAE specifically) experienced by the subject since informed consent was obtained.
- Alcohol swab or cleanse the area of vaccination (following the local standard of care), followed by IM injection into the deltoid with the designated study treatment.
- Monitoring for any AEs for approximately 30-60 minutes following vaccination.
- Vital sign (heart rate, blood pressure, respiratory rate, and axillary body temperature) and a fetal heart tone check performed at approximately 30 minutes (range 30-60 minutes) post-vaccination.
- Distribution of the subject diary and oral thermometer for documentation of any AEs (solicited and unsolicited), oral temperature and concomitant medications taken; and documentation of any unscheduled physician visit or hospitalization associated with an adverse event, occurring from the time of discharge through to Day 6 (inclusive). Diaries will provide a telephone number for 24-hour contact to the study staff in the event of concerns, solicited or unsolicited AEs, new obstetrical complications, or symptoms suggestive of an RSV infection.
- Issuance of a Study Identification Card that indicates the maternal subject is part of an investigational vaccine trial and provides the contact number(s) of the obstetrical investigator's study staff. The identification card will also include a list of the clinical signs and symptoms of an RSV infection in adults and infants.
- Instruction for subjects to inform the study site promptly of any severe (grade 3) solicited or unsolicited AE, obstetrical complication, or symptoms suggestive of an RSV infection.
- Verify subject locator information and the delivery center to be utilized.
- Schedule the next visit.

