7 LABORATORY REQUIREMENTS

[Appendix 3](#) specifies the maximum amount of blood that will be drawn from maternal (120 mL) and infant (from 3 to 6 mL, depending on the collection method) subjects, and from the cord blood at delivery (a minimum of 5 mL) for clinical safety and/or immunogenicity laboratory procedures to be completed throughout the study. This amount may increase for maternal subjects if repeat laboratory safety assessments are performed (see Section [8.2.3](#) for more details).

Specific information regarding the central or local laboratories that will perform clinical laboratory safety testing, RSV serology testing, and genotyping of respiratory specimens is provided in the **Study Operations Manual**.

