7.2 Assessments of Immunogenicity

Anti-F IgG antibody levels in EU, PCA concentrations, and neutralizing antibody titers to RSV/A and RSV/B will be determined at protocol-specified time points for all subjects. Completion of microneutralization testing may be staged, due to its cumbersome nature, and results may be reported in addenda to the primary clinical study report. Serological immunogenicity parameters will include GMEU, geometric mean concentration (GMC), or GMT (as appropriate); GMFR, SCR, and SRR by treatment group for most analyses. Comparisons across groups will be performed as described in the statistical analysis plan and briefly in Section [10.5](#). Blood samples from maternal subjects will be drawn for RSV serology testing at screening (Day -28 to 0) and on Day 14 prior to delivery, at delivery, and on Days 35 and 180 post-delivery. Blood samples from infant subjects will be drawn for RSV serology testing at post-delivery study Days 14 and 90 for Cohort 1 infants, on Days 35 and 120 for Cohort 2 infants, and on Days 60 and 180 for Cohort 3 infants. Infant subjects may also have blood drawn within 72 hours of birth if cord blood is not collected at delivery.

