11. IMMUNOGENICITY ANALYSES

Immunogenicity summaries and associated statistical analyses will be based primarily on the PP immunogenicity Populations, i.e., PP-IMM-M for maternal subjects and PP-IMM-I for infant subjects with supportive results derived from the ITT Populations, i.e., ITT-IMM-M for maternal subjects and ITT-IMM-I for infant subjects. No imputation for missing data will be performed. Data will be transformed as appropriate prior to analysis. Please refer to Section 16 for the handling of lower limit of quantitation (LLOQ) for the seroconversion (SCR, definition provided below) analysis.

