11.1.1. Anti-F IgG ELISA (EU)

The following parameters will be analyzed for maternal subjects.

- GMEU at baseline (pre-vaccination on Day 0) and post-vaccination on Day 14, at delivery, and postpartum on Days 35 and 180 (as applicable).
- GMFR_{Post/Pre} on post-vaccination Day 14, at delivery, and postpartum on Days 35 and 180 (as applicable).
- GMR_{Cord/MS} on the within-maternal-infant pair for cord blood over maternal serum (MS) at delivery, e.g., GMFR Transplacental Transfer Proportion.
- Seroconversion Rate (SCR) – defined as the proportion of subjects with ≥ 2 -fold and ≥ 4 -fold increases in concentration from baseline, calculated as the proportion (%) of subjects in a particular treatment group with a baseline concentration $<$ LLOQ and a post-vaccination concentration $\geq 2 \times$ LLOQ and $\geq 4 \times$ LLOQ, respectively, or a baseline concentration \geq LLOQ and a ≥ 2 -fold and ≥ 4 -fold, respectively, increase in

post-vaccination concentrations. These response rates will be summarized post-vaccination on Day 14, at delivery, and postpartum on Days 35 and 180 (as applicable).

- Seroresponse rate (SRR) – defined as the proportion (%) of subjects in the RSV F treatment group with an increase in antibody level over a specific time period which is greater than the 95th percentile of antibody response in the absence of active vaccine based on the behavior of placebo recipients' sera over the same period. SRR will be analyzed by computing the ratio (post-vaccination/pre-vaccination [Day 0]) at each post-vaccination time-point on Day 14, at delivery, and postpartum on Days 35 and 180 (as applicable). At a given time-point, the 95th percentile of the ratios in the placebo group will be estimated. A subject in any treatment group will be identified as a responder if its ratio is greater than the estimated threshold in the placebo group at the given time-point.

The following parameters will be analyzed for infant subjects:

- GMEU of anti-F IgG in cord blood and on D+14, D+35, D+60, D+90, D+112, and D+180.
- GMR_{AD/Cord} of anti-F IgG EU within-subject ratios after delivery (AD) on D+14, D+35, D+60, D+90, D+120, and D+180 over cord blood value at delivery.

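### SAP 16.2 ties the immunogenicity baseline to a day-of-vaccination sample, but the protocol's only pre-dose serology draw is at screening (Day -28 to 0)

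*SAP*

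**What the plan says.** SAP 16.2 contains two rules in consecutive sentences. The first covers all analyses: "baseline will be defined as the last non-missing measurement prior to the first administration of the study material". The second covers immunogenicity only: "For immunogenicity analysis, baseline will be the sample drawn prior to the first vaccination, on the day of vaccination".

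The protocol places the pre-dose draw at screening. Section 7.2 states: "Blood samples from maternal subjects will be drawn for RSV serology testing at screening (Day -28 to 0"). Section 6.1.1.2 lists the same draw among the screening procedures and itself calls it baseline: "For RSV baseline serology (20 mL"). In the Appendix 1 schedule, RSV serology is marked in the Day -28 to 0 column and not in the Day 0 column.

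For Day 0, Protocol 6.1.1.3 says that eligible women "will be randomized to a treatment group and infant serology cohort. The following procedures will then be performed". The list that follows covers the adverse event query, injection, monitoring, vital signs, diary, identification card, instructions and scheduling. It has no blood draw. Protocol 7 says that Appendix 3 "specifies the maximum amount of blood that will be drawn from maternal (120 mL").

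On missing values, SAP 11 says: "No imputation for missing data will be performed". SAP 11.1.1 builds the maternal seroresponse cut-off from post/pre ratios: "At a given time-point, the 95th percentile of the ratios in the placebo group will be estimated".

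**The concern.** A mother whose screening serology was drawn before Day 0 has a baseline under the first sentence of 16.2 and none under the second. If the second sentence is a deliberate exception, it does not fit the protocol's schedule. If it is not, it contradicts the sentence before it.

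The measures at stake are the maternal ones that divide by baseline: geometric mean fold-rise (GMFR), the 2-fold and 4-fold seroconversion rates (SCR), and the seroresponse rate (SRR). For SRR the loss goes beyond the individual. Only placebo mothers with a baseline contribute a ratio, so dropping some of them could also move the cut-off applied to everyone. Two programmers working from 16.2 could produce different tables.

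**Working it through.** **1. How many pre-dose serology draws exist.** Maternal venous volumes from Protocol Appendix 3:

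- Serology: screening (Day -28 to 0), Day 14, delivery, D+35 and D+180: 5 × 20 mL = 100 mL.
- Safety laboratory: screening and Day 14: 2 × 10 mL = 20 mL.
- Total: 100 + 20 = 120 mL, which reproduces the stated maximum.

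A separate Day 0 serology draw would give 6 × 20 + 20 = 140 mL, above that maximum. There is therefore one scheduled pre-dose draw, and it belongs to screening.

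**2. The two rules applied to that draw.**

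| Day of screening draw | 16.2, first sentence | 16.2, second sentence |
|---|---|---|
| Day -28 to -1 | baseline exists | no baseline |
| Day 0, before injection | baseline exists | baseline exists |

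Same-day screening is allowed but not required. For women in a country's first year, Protocol 6.1.1.2 recommends taking the safety-laboratory blood at least two days before vaccination, and Appendix 3 totals that blood with the serology sample as one 30 mL visit volume. The affected group is therefore unlikely to be empty, but its size cannot be derived.

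**3. Outputs that use the maternal baseline.**

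- Anti-F IgG and palivizumab-competitive antibody (PCA): 4 measures (GMFR, 2-fold SCR, 4-fold SCR, SRR) × 4 time-points × 2 assays = 32.
- RSV/A and RSV/B microneutralization (MN), at delivery only (SAP 11.1, Protocol 10.5): 4 × 1 × 2 = 8.
- Baseline levels themselves: 2 assays + 2 viruses = 4.
- Total: 32 + 8 + 4 = 44. If MN followed all four IgG time-points, as SAP 11.1.3 reads, it would be 32 + 32 + 4 = 68.

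**4. Precision under the literal rule (hypothetical).** Let *s* be the share of mothers sampled on Day 0. This is an assumption; no document gives it. Intervals widen by 1/√*s*. For a 50% SCR the 95% half-width is 1.96 × √(0.25/*n*), with *n* = *s* × the enrolment target (3,038 vaccine, 1,562 placebo).

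| *s* | widening | vaccine *n* | half-width (points) | placebo *n* | half-width (points) |
|---|---|---|---|---|---|
| 100% | 1.00 | 3,038 | 1.8 | 1,562 | 2.5 |
| 90% | 1.05 | 2,734 | 1.9 | 1,406 | 2.6 |
| 50% | 1.41 | 1,519 | 2.5 | 781 | 3.5 |
| 25% | 2.00 | 760 | 3.6 | 390 | 5.0 |
| 10% | 3.16 | 304 | 5.6 | 156 | 7.8 |

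**The case against.** The best defence is that the literal reading is not the intended one. A specific rule after a general one is ordinary drafting. The clause refers to the sample drawn before vaccination, and the protocol schedules exactly one, so the day is arguably a wrong description of an identifiable sample. Other SAP text leans the same way. Section 11.1 describes baseline as pre-vaccination without naming a day, 16.6 selects one sample per visit, and 5.3.3.1 judges whether a sample was provided by the protocol's visit windows. Sections 7 and 12.9 use Day 0 as a nominal label; 12.9 describes laboratory change both from Day 0 and from screening. The Day 0 phrases in 11.1.1 are therefore weak evidence.

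Much of this stands as a limit on the consequences. It does not remove the defect. The clause in 16.2 is not a nominal label; it states a calendar condition. None of the other sections defines baseline, and 16.2 does.

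The objections to the size also stand. *s* is assumed, and taking it as equal in both arms is a simplification, because early blood sampling is recommended only for first-year subjects and allocation changed from 1:1 to 2:1 after the first global season. The *n* values are enrolment targets, not the per-protocol immunogenicity population. MN may be run on a subset only, so the half-widths need not apply there. A count of table cells is not an effect size.

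**Conclusion.** The concern holds. The second sentence of 16.2 is wrong as written: it requires a same-day sample that the protocol does not require, and it departs from the all-analyses rule just before it.

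The practical effect is bounded. It ranges from nil, if the screening sample is used regardless, to the loss of fold-rise, seroconversion and seroresponse results for every mother sampled before Day 0. The widths above are illustrations over an assumed *s*, not estimates.

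Protocol 10.5 makes the affected outputs descriptive. Efficacy, infant serology and cord/maternal ratios do not use this baseline. Neither do the correlate-of-risk markers (cord, infant, and maternal Day 14 and delivery levels) or the infant decay model. Membership of the maternal per-protocol immunogenicity population is probably protected by the visit-window language in 5.3.3.1, so exclusion from it should not be presumed. The draw precedes randomization, and no bias between arms is claimed.

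The correction should be made: the textual conflict is certain and the remedy costs almost nothing.

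**What to change.** Delete the second sentence of SAP 16.2, which leaves the general rule in force, or replace it with: *For immunogenicity, baseline is the last serology sample collected before vaccination (scheduled at screening, Day -28 to 0).* The window there describes the schedule and is not an exclusion. A pre-dose sample taken before Day -28 would still be the baseline, as the first sentence of 16.2 implies, and would remain subject to the out-of-window judgement in 5.3.3.1.

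For consistency, change the two Day 0 labels in 11.1.1 (the baseline level and the seroresponse ratio) to baseline (pre-vaccination).

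The cost is SAP wording only: one sentence and two labels, with no new samples or data collection. If the screening sample is used without this edit, the departure from 16.2 would have to be described in the final study report, as SAP 14.1 requires.
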